8.3 Risks Associated with Participation in the Clinical Investigation

All assessments are considered to be standard of care but may be conducted more frequently to comply with the follow-up visit schedule. Non-invasive assessments at follow-up visits include physical exams, ABI/TBI, Rutherford Category assessments, and duplex ultrasounds. All pose minimal risk to the patient. For procedure-related risks, please refer to the current IFUs.

Risks associated with the management of privacy and confidentiality with the sharing of data exist for subjects participating in research studies. To mitigate these risks, each subject in the study will be assigned a specific study identification code that shares no identifiable factors with the Sponsor. Only hospital staff and the CRO will be privy to information that links the subject's identifiable information to this subject code. De-identified data (data that is attributed to the subject's study identification code) will be uploaded into a password protected Electronic Data Capture (EDC) system. This EDC can only be accessed by suitably trained and allocated members of the study team (site Investigators, Study Coordinators, personnel associated with the CRO and relevant personnel at the Sponsor organization).

8.4 Possible Interactions with Concomitant Medical Treatments

There are no known possible interactions within this study.

 SHOCKWAVE <small>MEDICAL INC</small>	No.: CP 67398	REV. C
	TITLE: FORWARD PAD IDE Study Protocol	
	CLASS: CLINICAL PROTOCOL	PAGE 34 OF 65

8.5 Mitigation of Risks

Only those patients meeting each inclusion and no exclusion criteria will be enrolled into this study. Investigators will be qualified by education, training and experience to assume responsibility for the proper conduct of the clinical investigation. Risks of observed or theoretical adverse events will be mitigated through the Instructions for Use, physician training, patient selection in the study protocol, and close monitoring of protocol adherence.

All efforts will be made to minimize risks specifically by:

- Site selection
- Ensuring compliance to the protocol and IFU
- Assignment of study identification code to protect privacy and ensure confidentiality
- Study monitoring
- Safety processes – protocol adverse event reporting requirements, CEC and DSM oversight, and safety reporting to regulatory authorities including Vigilance reporting
- Review of all device malfunctions and complaints by Quality. Risk acceptability thresholds and trend identification methods have been established, and actions will be taken if those are met.

 SHOCKWAVE <small>MEDICAL INC</small>	No.: CP 67398	REV. C
	TITLE: FORWARD PAD IDE Study Protocol	
	CLASS: CLINICAL PROTOCOL	PAGE 35 OF 65

9.0 DATA ANALYSIS PLAN

9.1 General Statistical Methods

Data from subjects enrolled under the US IDE protocol will be pooled with data from the Mini S Study. Results for the first 90 consecutively enrolled subjects (with a minimum of 50% of subjects enrolled in the US) including a minimum of 15 BTK lesions, across both studies will comprise the primary analysis cohort and will be submitted to support a Premarket Notification 510(k) submission.

The Mini S Study is being conducted in Australia and New Zealand. The Mini S Study and the FORWARD PAD IDE Study protocols share the same eligibility criteria, data collection requirements and IVL treatment algorithm. Both studies utilize the same electronic data capture system, are monitored with 100% source document verification, and include an independent angiographic core lab, independent clinical events committee (CEC) for endpoint adjudication of MAE and data safety monitor (DSM). Both studies use the XTR and FLX configurations of the JAVELIN IVL Catheter.

The statistical analysis plan (SAP) outlines the data and procedures used for assessing the safety and effectiveness of the Shockwave Medical JAVELIN catheter over pooled data from the two studies CP65324 (Mini S Study) and CP67398 (FORWARD PAD IDE).

Statistical analyses will be performed using SAS System® Version 9.4 or higher.

9.2 Primary Endpoints

9.2.1 Primary Safety Endpoint

Major Adverse Events (MAE) at 30 days defined as a composite of:

- All-cause death
- Clinically-driven target limb revascularization (CD-TLR)
- Unplanned target limb major amputation (above the ankle)

SAEs will be reviewed and adjudicated by the CEC. Only those adjudicated as MAEs will comprise the composite safety endpoint.

MAEs will be assessed on a per-subject basis.

The upper bound for the one-sided 95% Clopper-Pearson exact confidence interval will be reported for the MAE rate.

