2.0 STUDY SUMMARY

Study Title	Forward-Shifted Intravascular Lithotripsy (IVL) Technology in a Prospective, Multi-center, Single-arm Investigational Device Exemption (IDE) Study (FORWARD PAD IDE Study)
Study Objective	To assess the safety and effectiveness of the Shockwave Medical JAVELIN Peripheral IVL System for the treatment of heavily calcified, stenotic peripheral arteries.
Study Device(s)	Shockwave Medical Peripheral IVL System with JAVELIN IVL Catheter (XTR and FLX configurations)
Indication for Use	The Shockwave Medical IVL System is intended for lithotripsy-enhanced treatment of lesions, including calcified lesions, to increase luminal diameter, allowing for further treatment (e.g. post-dilatation) in the peripheral arterial vasculature. Not for use in the coronary or cerebral vasculature.
Study Design	Prospective, multi-center, single-arm IDE study
Enrollment	Up to 75 subjects at up to 20 sites in the United States. A minimum of 15 below-the-knee (BTK) lesions are required and a maximum of two (2) target lesions may be treated per subject.
Study Duration / Follow-Up Period	Subjects will be followed through discharge, 30 days, 6 and 12 months. Duplex Ultrasound (DUS) assessments required at 12 months. Total anticipated study duration approximately 33 months.
Subject Population	Subjects with moderate to severely calcified peripheral artery disease (PAD) with target lesion located in a native, de novo superficial femoral, popliteal or infrapopliteal artery.
Primary Safety Endpoint	Major Adverse Events (MAE) at 30 days defined as a composite of: 
 ○ Cardiovascular death ○ Clinically-driven target lesion revascularization (CD-TLR) ○ Unplanned target limb major amputation (above the ankle)
Primary Effectiveness Endpoint	Technical Success defined as final residual stenosis $\leq 50\%$ without flow-limiting dissection (\geq Grade D) of the target lesion by angiographic core lab.

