Limb Ischemia: Deficient supply of oxygenated blood to the tissues in the limbs that is due to obstruction of the inflow of arterial blood characterized by pain and/or discoloration of the limb.

Lithotripsy: A medical procedure for disrupting calculus in the body.

 SHOCKWAVE <small>MEDICAL INC</small>	No.: CP 67398	REV. C
	TITLE: FORWARD PAD IDE Study Protocol	
	CLASS: CLINICAL PROTOCOL	PAGE 57 OF 65

Luminal Patency: Post-procedure residual stenosis <50% as determined by investigator visual assessment or quantitative analysis of the end of procedure angiogram.

Major Adverse Event (MAE): For the purposes of this study, the definition of Major Adverse Event(s) includes:

- cardiovascular death
- target lesion revascularization
- Unplanned target limb major amputation (above the ankle)

Perforation: Puncture of an arterial wall.

Restenosis: Reoccurrence of narrowing or blockage of target lesion.

Rutherford Classification of Critical Limb Ischemia: Clinical staging system for describing PAD. It includes 7 categories:

Grade	Category	Clinical Description
0	0	Asymptomatic
I	1	Mild claudication
	2	Moderate claudication
	3	Severe claudication
II	4	Ischemic rest pain
	5	Ischemic ulceration not exceeding ulcer of the digits of the foot
IV	6	Severe ischemic ulcers or frank gangrene

(ACC/AHA/SCAI/SIR/SVM 2018 Appropriate Use Criteria for Peripheral Artery Intervention – Bailey et al. 2019)

Serious Adverse Device Effect (SADE): Adverse device effect that has resulted in any of the consequences characteristic of a serious adverse even.

Serious Adverse Event (SAE): Adverse event that led to any of the following:

 SHOCKWAVE <small>MEDICAL INC</small>	No.: CP 67398	REV. C
	TITLE: FORWARD PAD IDE Study Protocol	
	CLASS: CLINICAL PROTOCOL	PAGE 58 OF 65

- death,
- serious deterioration in the health of the subject, user, or other persons as defined by one or more of the following:
 - a life-threatening illness or injury, or
 - a permanent impairment of a body structure or a body function including chronic diseases, or
 - in-patient or prolonged hospitalization, or
 - medical or surgical intervention to prevent life-threatening illness or injury, or permanent impairment to body structure or a body function,
 - fetal distress, fetal death, a congenital abnormality, or birth defect including physical or mental impairment.

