Note: Planned hospitalization for a pre-existing condition, or a procedure required by the CIP, without serious deterioration in health, is not considered a serious adverse event.

Target Lesion Revascularization, Clinically-driven (TLR): A target lesion revascularization performed due to target lesion diameter stenosis $\geq 50\%$ and either evidence of clinical or functional ischemia (e.g., recurrent/progressive life-limiting intermittent claudication, claudication unresponsive to medical therapy, CLI) or recurrence of the clinical syndrome for which the initial procedure was performed. Clinically-driven target lesion revascularization (CD-TLR) occurs in the absence of protocol directed surveillance ultrasound or angiography.

Target Vessel Revascularization, Clinically-driven (TVR), non-TLR: A target vessel revascularization performed due to non-target lesion diameter stenosis $\geq 50\%$ and either evidence of clinical or functional ischemia (e.g., recurrent/progressive life-limiting intermittent claudication, claudication unresponsive to medical therapy, CLI) or recurrence of the clinical syndrome for which the initial procedure was performed. Clinically driven target vessel revascularization occurs in the absence of protocol directed surveillance ultrasound or angiography.

Total Occlusion A 100% stenotic lesion as documented by angiographic absence of flow.

Toe Brachial Index (TBI): The ratio of systolic blood pressure measured at the toe to systolic blood pressure measured at the brachial artery.

Unanticipated Serious Adverse Device Effect (USADE): Serious adverse device effect which by its nature, incidence, severity or outcome has not been identified in the current risk assessment.

Note: Anticipated serious adverse device effect (ASADE) is an effect which by its nature, incidence, severity or outcome has been identified in the risk assessment.

Wound: Foot ulcer or gangrene. After debridement and/or minor amputation, a wound is characterized as a healed wound when it is completely epithelialized.

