2. STUDY OBJECTIVE

The objective of this Clinical Proposal is to use the data that Shockwave Medical is currently collecting from the two clinical studies described above to demonstrate the safety and effectiveness of the Shockwave Medical JAVELIN Peripheral IVL Catheter compared to pre-defined performance goals. This document may modify and supersede the statistical plans outlined in the respective study protocols.

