4.1. Primary Safety Endpoint

The primary safety endpoint for the pooled cohort is Major Adverse Events (MAE) at 30 days defined as a composite of:

- Cardiovascular death
- Unplanned target limb major amputation (above the ankle)
- Clinically-driven target lesion revascularization (CD-TLR)

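### Protocol 9.2.1 defines the primary 30-day MAE with all-cause death and target limb revascularization; Protocol 2.0, Protocol 5.1 and SAP 4.1 use cardiovascular death and target lesion revascularization.

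*Protocol*

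**What the plan says.** Protocol 9.2.1 lists three components for the primary 30-day MAE: "All-cause death", "Clinically-driven target limb revascularization (CD-TLR") and unplanned major amputation of the target limb. It then gives a counting rule: "Only those adjudicated as MAEs will comprise the composite safety endpoint".

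Protocol 2.0 and Protocol 5.1 list cardiovascular death, "Clinically-driven target lesion revascularization (CD-TLR") and the same amputation component. SAP 4.1 gives this composite for the pooled cohort, starting with "Cardiovascular death".

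On precedence, SAP section 2 says: "This document may modify and supersede the statistical plans outlined in the respective study protocols".

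The glossary in Protocol 15.1 has an MAE entry ("For the purposes of this study, the definition of Major Adverse Event(s) includes") that names cardiovascular death and target lesion revascularization but leaves out the clinically-driven qualifier. Its only entry for target lesion revascularization is "Target Lesion Revascularization, Clinically-driven (TLR"). The same glossary limits an unplanned amputation to the first 30 days after the index procedure. SAP 10.3 refers readers to the protocol glossary.

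**The concern.** Two of the three components of a primary endpoint differ between current sections. The difference is in the Rev. C body text, not in the revision history. Section 9.2.1 belongs to the Data Analysis Plan and says which adjudicated events count, so it cannot be dismissed as background.

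The events that separate the two definitions are a non-cardiovascular death and a clinically-driven reintervention elsewhere in the target limb. Both will be on record: the CEC adjudicates deaths, revascularizations and amputations (Protocol 13.1), and angiograms from any target limb revascularization go to the core lab (Protocol 7.8.5). The definition alone decides whether they enter the numerator.

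This is a single-arm test against a fixed goal, and study success requires both primary endpoints. If the reading is chosen after the events are known, the choice will look driven by the result, and a 510(k) submission rests on it.

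A second, smaller problem lies in the secondary endpoints. Protocol 5.1 and SAP 4.3 call for MAE at 6 and 12 months, with amputation as a component. Read literally, the 30-day limit in the glossary removes every later major amputation from those composites. SAP Appendix A, which counts amputations within each reporting period, also points away from a fixed 30-day limit.

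**Working it through.** **Inputs** (Protocol 9.3; SAP 6.1 to 6.3): n = 90; safety goal 11.2%; expected MAE rate 2.0%; effectiveness goal 85.0%; expected technical success 97.0%; one-sided exact binomial tests at 0.025. I take all 90 subjects as evaluable.

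**1. The plan's own figures.** Safety passes at the largest c with P(X ≤ c | 90, 0.112) ≤ 0.025.

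| MAEs in 90 | p-value against 11.2% | Two-sided 95% Clopper-Pearson upper limit | Result |
|---|---|---|---|
| 4 | 0.0218 | 10.99% | pass |
| 5 | 0.0537 | 12.49% | fail |

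So c = 4. Safety power is P(X ≤ 4 | 90, 0.02) = 0.9652 (stated 96.5%). Effectiveness passes at 84 or more successes in 90 (p = 0.0131), with power 0.9812 at 97% (stated 98.1%). Joint power is 0.9652 × 0.9812 = 0.9471 (stated 94.7%). All three figures reproduce.

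**2. Direction of the difference.** Every cardiovascular death is a death from any cause, and every clinically-driven target lesion revascularization is a revascularization of the target limb. The 9.2.1 count is therefore at least the SAP 4.1 count in any data set.

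**3. The knife edge.** If the SAP 4.1 count is 4, one further subject with an event that counts only under 9.2.1 makes it 5, and pass becomes fail. At the planned 2.0% rate, P(X = 4) = 0.0719, or 7.2%.

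**4. Probability of opposite verdicts.** Let d be the proportion of subjects whose only event counts under 9.2.1 alone. The documents give no value for d, so the values below are assumptions. Because the counts are nested,

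P(narrow ≤ 4 and broad ≥ 5) = P(X ≤ 4 | 0.02) − P(X ≤ 4 | 0.02 + d).

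| d (assumed) | Broad rate | P(X ≤ 4), broad | Opposite verdicts | Joint power if 9.2.1 governs |
|---|---|---|---|---|
| 0.1 points | 2.1% | 0.9585 | 0.7% | 94.1% |
| 0.25 points | 2.25% | 0.9471 | 1.8% | 92.9% |
| 0.5 points | 2.5% | 0.9245 | 4.1% | 90.7% |
| 1.0 points | 3.0% | 0.8659 | 9.9% | 85.0% |
| 2.0 points | 4.0% | 0.7080 | 25.7% | 69.5% |

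For example, at d = 1.0 points: 0.9652 − 0.8659 = 0.0993, and joint power is 0.8659 × 0.9812 = 0.8496.

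**5. Amputation window.** A limit of 30 days cannot remove an event from a 30-day endpoint, so the primary test is untouched. Only the 6- and 12-month MAE are affected.

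**The case against.** The strongest reply is that the tested analysis already has one definition. The hypothesis is tested in the pooled cohort, the protocol refers to the SAP for that analysis, and SAP 4.1 defines the endpoint for it. Protocol 2.0, 5.1 and the glossary agree with the SAP on cardiovascular death and on the lesion, so 9.2.1 stands alone. The word limb in 9.2.1 also looks like a slip: the abbreviation CD-TLR is kept, and Protocol 15.1 and 15.2 define it only at lesion level. I accept that SAP 4.1 is probably the governing text and that the revascularization half may be a drafting error. Neither point disposes of the death component, and a permissive sentence in the SAP does not repair a contradiction inside the protocol.

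The second reply is that the extra events should be rare within 30 days. Life expectancy must exceed one year, recent infarction or stroke is excluded, and the glossary counts as cardiac any death in which a cardiac cause cannot be ruled out. This is fair, and it is why the table starts at 0.1 points. The 25.7% figure would need an extra rate equal to the whole planned rate.

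Two further points stand in part. Mini S events are already being reported, so the realistic deadline is the primary analysis. And SAP 5.1 derives the 11.2% goal from the earlier 8.7% goal without listing that endpoint's components, so the documents do not show which composite the goal was built on.

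**Conclusion.** The concern holds. The primary safety endpoint has two incompatible definitions in current text, and the broader one sits in the protocol's own analysis section. No stated sample size or power figure is wrong: 96.5% and 94.7% are correct for a 2.0% rate, but nothing in the documents says that rate applies to the broader composite. The pass mark is 4 events in 90, so one subject can separate the two verdicts. The chance of disagreement runs from 0.7% to 25.7% as the assumed extra rate goes from 0.1 to 2.0 percentage points, with a narrow rate of 2.0% and 90 evaluable subjects. The unplanned-amputation wording is a separate, lesser defect confined to the 6- and 12-month MAE. The missing clinically-driven qualifier in the glossary MAE entry is probably a loose restatement of the narrower composite. The primary definition must be made unique before the primary analysis.

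**What to change.** 1. Correct Protocol 9.2.1 and the glossary MAE entry to the composite in Protocol 2.0, Protocol 5.1 and SAP 4.1: cardiovascular death, revascularization of the target lesion that is clinically driven, and unplanned major amputation of the target limb. Do this before further adjudication if possible, and in any case before the primary analysis. When doing so, confirm that this composite matches the one behind the 8.7% goal in SAP 5.1.
2. Remove the 30-day limit from the glossary entry for unplanned amputation, so that each reporting time point sets its own window.
3. Optional: align the glossary's cardiac death entry with the term cardiovascular death, and report the broader 9.2.1 composite as a sensitivity analysis.

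The cost is wording in the protocol, and in the CEC charter if it repeats the text, plus one table if the sensitivity analysis is done. No patients or procedures are added, and the planned sample size and power stay as stated.

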7.8.5 Prior to Target Limb Revascularization

If a target limb revascularization procedure is performed during the follow-up period, angiographic images acquired as standard of care should be submitted to the core lab for purposes of adjudication.

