10.1.2 Serious Adverse Event (SAE)

Adverse event that led to any of the following

- a) death,
- b) serious deterioration in the health of the subject, users, or other persons as defined by one or more of the following:
 - 1) a life-threatening illness or injury, or
 - 2) a permanent impairment of a body structure or a body function including chronic diseases, or
 - 3) in-patient or prolonged hospitalization, or
 - 4) medical or surgical intervention to prevent life-threatening illness or injury, or permanent impairment to a body structure or a body function,
- c) fetal distress, fetal death, a congenital abnormality, or birth defect including physical or mental impairment.

Note: Planned hospitalization for a pre-existing condition, or a procedure required by the CIP, without serious deterioration in health, is not considered a serious adverse event.

 SHOCKWAVE <small>MEDICAL INC</small>	No.: CP 67398	REV. C
	TITLE: FORWARD PAD IDE Study Protocol	
	CLASS: CLINICAL PROTOCOL	PAGE 39 OF 65

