10.4.2 SAE Reporting Requirements

Any AE meeting any of the criteria for an SAE occurring at any time during the study (enrollment through 12 months) must be reported to the Study Sponsor within 2 business days after the designated study site personnel first learns of the event. The SAE must also be reported to the IRB per the institution's policy for reporting SAEs. SAEs should be reported in the subject's medical records as applicable and on the Adverse Event Case Report Form (AE CRF). Data reported should include date of onset, treatment, resolution, and an assessment of both seriousness and relationship to the study device and procedure. SAEs will be followed until the event has resolved (in the case of permanent impairment, the event will be followed until it stabilizes, and the overall clinical outcome has been ascertained).

It is the responsibility of the Investigator to inform their IRB of serious adverse events as required by their local IRB policies. The Investigator should forward a copy of this report to the Study Sponsor and file in the site regulatory binder.

The Clinical Events Committee (CEC) will review and adjudicate SAEs. See section 13.1 for information on the CEC.

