13.0 STUDY COMMITTEES

13.1 Clinical Events Committee (CEC)

To meet the ethical responsibilities and standards for research subjects, an independent Clinical Events Committee shall serve as forum for adjudication of certain pre-specified clinical event types, including SAEs, as described in the CEC charter.

The CEC will be managed [REDACTED]

In order to enhance objectivity and reduce the potential for bias, the CEC shall be independent of the Study Sponsor as well as the study investigators.

The CEC is made up of clinicians with pertinent expertise who are not participants in the study and who do not have any other real or potential conflicts of interest. Members have expertise in peripheral endovascular procedures, are experienced in the conduct of controlled clinical trials and have knowledge of bioethics and integrity related to the duties and responsibilities to be performed.

The CEC is charged with the development of specific criteria used for the categorization of adverse events and clinical endpoints in the study. Criteria will be established for selected complications and clinical events. Events to be adjudicated include death, MAEs, revascularizations, and amputations. The CEC will also adjudicate relationship to the study device and study procedure according to the following classifications: definitely related, probably related, possibly related, unlikely related and not related.

At the onset of the study, the CEC will establish explicit rules outlining the minimum amount of data required and the algorithm followed in order to classify an event. The methodology for performing these responsibilities shall be developed and outlined in the CEC Charter. Operational provisions shall be established to minimize potential bias (i.e., CEC members shall be blinded to the clinical site to the extent possible during adverse event review and adjudication). The methodology for performing these responsibilities shall be developed and outlined in the CEC Charter. In addition, the CEC Charter will include the number of members, responsibilities, CEC meeting procedures, and meeting frequency.

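### Protocol 9.2.1 admits only SAEs to the 30-day MAE composite, while Protocol 13.1 and the SAP set no seriousness condition; read literally, 9.2.1 could omit a non-serious CD-TLR

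*Protocol*

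**What the plan says.** **Rule for the composite.** Protocol 9.2.1: "SAEs will be reviewed and adjudicated by the CEC. Only those adjudicated as MAEs will comprise the composite safety endpoint". Protocol 10.4.2 describes the same flow of events: "The Clinical Events Committee (CEC) will review and adjudicate SAEs".

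**What makes an event serious.** Protocol 10.1.2 requires death, a serious deterioration in health, or a fetal or congenital outcome. Serious deterioration covers a threat to life, lasting impairment, an in-patient or prolonged stay, or an intervention needed to avert a threat to life or lasting impairment. A note adds: "Planned hospitalization for a pre-existing condition, or a procedure required by the CIP, without serious deterioration in health, is not considered a serious adverse event". No text classes every revascularization as serious.

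**What makes a CD-TLR.** Protocol 15.1 asks for stenosis of at least 50% together with either clinical or functional ischemia, for which claudication is among the examples, or "recurrence of the clinical syndrome for which the initial procedure was performed". Seriousness is not part of the definition. Rutherford categories 2 and 3 (moderate and severe claudication) are eligible under Protocol 7.2.1.

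**The other route.** Protocol 13.1 describes the CEC's task as "adjudication of certain pre-specified clinical event types, including SAEs, as described in the CEC charter" and then states: "Events to be adjudicated include death, MAEs, revascularizations, and amputations". SAP 4.1 defines 30-day MAE with CD-TLR as a component. SAP 4 has one CEC adjudicate all endpoints in both studies. SAP Appendix A lists repeat target-lesion revascularization as a clinical endpoint in its own right. None of these carries an SAE filter.

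**The concern.** The same event can be in or out of the primary safety endpoint depending on which section is followed. Under 9.2.1 the answer turns on the site's seriousness classification and on the care setting; under 13.1 and the SAP it turns on the endpoint definition.

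The error has one direction. An SAE filter can remove MAE subjects but never add them, so it lowers the observed rate against a performance goal. The study has no control arm in which the same loss would occur, and success requires this endpoint to be met.

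**Working it through.** **Step 1. Can a CD-TLR be non-serious?** Take a Rutherford 2 or 3 subject whose claudication recurs within 30 days and whose target lesion, with at least 50% stenosis, is re-treated as a same-day outpatient.

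| Test | Met? |
|---|---|
| CD-TLR (Protocol 15.1) | Yes |
| Death or threat to life (10.1.2) | No |
| Lasting impairment, or intervention to avert it (10.1.2) | Not clearly |
| In-patient or prolonged stay (10.1.2) | No |

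So the event qualifies for the endpoint without a clear reason to be reported as an SAE. The other two components are not exposed in practice. A death is always an SAE, and a major amputation meets the lasting-impairment criterion.

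**Step 2. Inputs for the size** (Protocol 9.3 and SAP 6.1): n = 90, goal 11.2%, expected rate 2.0%, one-sided exact binomial test at 0.025, stated power 96.5%. All 90 subjects are taken as evaluable.

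**Step 3. Reproduce the plan.** The safety goal is met if X ≤ c, where c is the largest integer with P(X ≤ c | 90, 0.112) ≤ 0.025.
- P(X ≤ 4 | 90, 0.112) = 0.0218 and P(X ≤ 5 | 90, 0.112) = 0.0537, so c = 4.
- Power = P(X ≤ 4 | 90, 0.02) = 0.9652, which matches 96.5%.
- The effectiveness rule of at least 84/90 has power 0.9812. The product 0.9652 × 0.9812 = 0.9471 matches the stated 94.7%.
- Exact upper 97.5% limits: 4/90 gives 10.99% (pass) and 5/90 gives 12.49% (fail). The one-sided 95% limit that 9.2.1 asks to be reported leads to the same cut-off: 9.88% and 11.33%.

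**Step 4. Effect of missed subjects.** Let m be the share of MAE subjects not counted because their only event was classed as non-serious. The chance of passing is P(X ≤ 4 | 90, p(1 − m)), where p is the true MAE rate. At p = 2% and m = 20%, for example, the counted rate is 0.02 × 0.8 = 0.016. The documents give no value for m, so the values below are assumptions.

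| m | p = 2% | p = 5% | p = 8% | p = 11.2% |
|---|---|---|---|---|
| 0% | 96.5% | 53.0% | 14.5% | 2.2% |
| 10% | 97.6% | 61.9% | 21.6% | 4.4% |
| 20% | 98.5% | 70.8% | 31.0% | 8.6% |
| 30% | 99.1% | 79.2% | 42.8% | 15.7% |

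**Step 5. One missed subject.** A single omission reverses the result only if exactly five subjects truly have an MAE and one is not counted. At the planned rate, P(X = 5) = 0.9904 − 0.9652 = 0.0252; at 11.2% it is 0.0537 − 0.0218 = 0.0319.

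**The case against.** The case on the other side is substantial.

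- **The SAP governs the pooled analysis.** SAP 2 says that it may modify and supersede the protocols' statistical plans, and it defines and counts MAE without an SAE condition. This largely stands. But the SAP does not withdraw the restriction in 9.2.1 or say which reports reach the CEC, and its own counting relies on adjudicated events.
- **Capture does not depend on seriousness.** Protocol 10.4.1 collects all adverse events through 12 months, 9.1 states full source verification, and 13.1 names revascularizations for adjudication. For later target-limb procedures, 7.8.5 adds that "angiographic images acquired as standard of care should be submitted to the core lab for purposes of adjudication". A non-serious event should therefore be in the database. That makes the repair easy, but it does not remove the limiting words in 9.2.1. The sentence in 10.4.2 is not exclusive on its own and can be read alongside 13.1.
- **The scenario is narrow.** It needs a repeat target-lesion procedure within 30 days, done as an outpatient, reported as non-serious and then kept out of the composite. This stands and limits the size.

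A reader might infer that qualifying CD-TLRs will in fact be lost. The documents do not support that: 13.1 and the SAP point the other way, and the CEC charter, to which 13.1 defers, is not among the documents.

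A reader might also take the planned-hospitalization note as a second way out of SAE status. It is weak: it applies only without serious deterioration in health, and exclusion criterion 2 bars target-limb procedures already planned within 30 days of the index procedure.

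Nor does the longer deadline for non-serious events in Protocol Table 3 decide the count. Those events are still reported.

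**Conclusion.** The point holds as an internal contradiction about what enters the primary safety endpoint, not as a confirmed gap in ascertainment. Protocol 9.2.1, with 10.4.2 describing the same feed, restricts the composite to SAEs; 13.1 and the SAP do not. Only CD-TLR is realistically exposed, and any omission would favour meeting the goal.

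If the device performs as planned, the consequence is small: about 2 percentage points in the chance of passing at m = 20%. It is larger where the goal is meant to protect, at a true rate near 11.2%, where the false-pass chance goes from 2.2% to 8.6% at the same m. Those figures should not be read as estimates of the study's actual error rate. They assume a true rate at the goal, and they apply the assumed loss to the whole composite although only non-serious CD-TLR could be missed. The design figures themselves (cut-off 4/90, power 96.5%, joint power 94.7%) reproduce and are unaffected.

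**What to change.** Reword Protocol 9.2.1 and 10.4.2 along these lines: *All deaths, target-limb revascularizations and target-limb amputations, whether or not reported as serious, are adjudicated by the CEC. All those adjudicated as MAE components count in the composite.* State that the rule applies to both pooled studies, and confirm that the CEC charter uses the same triggers. This brings 9.2.1 and 10.4.2 into line with 13.1 and the SAP.

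The cost is a wording change in two sections. Protocol 13.1 already lists these events, so the added adjudication is negligible. The observed MAE rate may be slightly higher. Sample size, cut-off and power do not change. Moving these events to the 2-business-day row of Protocol Table 3 is optional: it would speed up review but is not needed for a correct count.
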